## **6.4 Study Intervention Compliance**

When patients self-administer study interventions at home, compliance with study intervention will be assessed at each visit. Compliance will be assessed by counting of returned tablets during the site visits and documented in the source documents and eCRF. Patients should return all unused medication and empty containers to the investigator.

Deviation(s) from the prescribed dosage regimen should be recorded in the eCRF.

A record of the number of savolitinib and osimertinib/placebo tablets dispensed to and taken by each patient must be maintained and reconciled with study intervention and compliance records. Intervention start and stop dates, including dates for intervention delays and/or dose reductions will also be recorded in the eCRF.

## **6.5 Concomitant Therapy**

Any medication or vaccine (including over-the-counter or prescription medicines, vitamins, and/or herbal supplements or other specific categories of interest) that the patient is receiving at the time of enrolment or receives during the study must be recorded along with:

- Reason for use
- Dates of administration including start and end dates
- Dosage information including dose and frequency

The Medical Monitor should be contacted if there are any questions regarding concomitant or prior therapy.

For patients continuing treatment with osimertinib during Screening, the date and time of administration of the last dose of osimertinib prior to Cycle 1 Day 1 (prior to PK sampling) should be recorded.

Medication other than that described in [Appendix J](#), which is considered necessary for the patient's safety and wellbeing, may be given at the discretion of the investigator and recorded in the appropriate sections of the eCRF.

Guidance on medicines to avoid, medications that require close monitoring, and washout periods is provided in [Appendix J](#) and a list of medicines to avoid is kept up to date at the following: <http://medicine.iupui.edu/clinpharm/ddis/main-table>.

The use of medications listed in [Table 6](#) is restricted, these medications are permitted with caution and careful monitoring of patients.

**Table 6 Restricted Medications**

Medication/class of drug	Usage (including limits for duration permitted and special situations in which it's allowed)
Statins	Discontinuation of statins is advised unless considered essential, in which case, the patients should be prescribed the lowest dose available and monitored for the effects of increased statin exposure.
Paracetamol	The administration of acetaminophen (paracetamol) to a patient is restricted to 3 g per day or the maximum dose approved locally (if less than 3 g/day) during the study.
Sensitive CYP2C8 substrates	Those drugs defined as sensitive CYP2C8 substrates (almost exclusively metabolised by CYP2C8, such as repaglinide and rosiglitazone) should be used with caution.
Drugs affected by P-glycoprotein	Drugs that are known to be affected by P-glycoprotein such as digoxin, quinidine, loperamide, ritonavir and saquinavir should be used with caution.
Metformin	Use with caution, monitor patients for the effect of increased metformin exposure.
Adefovir, lamivudine, and tenofovir	Use with caution, monitor patients for the effect of increased exposure.
Drugs whose disposition is dependent upon the BCRP	
Patients taking concomitant medications whose disposition is dependent upon the BCRP and with a narrow therapeutic index should be closely monitored for signs of changed tolerability as a result of increased exposure of the concomitant medication whilst receiving osimertinib.
 
Patients taking rosuvastatin should have creatine phosphokinase levels monitored (due to BCRP-mediated increase in exposure). If the patient experiences any potentially relevant AEs suggestive of muscle toxicity including unexplained muscle pain, tenderness, or weakness, particularly if accompanied by malaise or fever, rosuvastatin must be stopped and any appropriate further management should be taken.

Drugs prolonging QT interval	
The concomitant administration of drugs known to prolong QT interval is restricted unless considered essential due to patient management, in which case, patients should be closely monitored with more frequent ECGs. Additional guidance on drugs known to prolong QT interval is provided in Appendix J.
 
The following drugs are known to prolong QT interval or induce Torsades de Pointes and should not be combined with osimertinib:
 
Clarithromycin, droperidol, erythromycin, procainamide, cisapride, disopyramide, dofetilide, domperidone, ibutilide, quinidine, sotalol, sparfloxacin, thioridazine, bepridil, chlorpromazine, halofantrine, haloperidol, mesoridazine, levomethadyl, methadone, pimozide, arsenic trioxide, pentamidine, amiodarone, chloroquine (Appendix J).

**Table 6 Restricted Medications**

Medication/class of drug	Usage (including limits for duration permitted and special situations in which it's allowed)
Drugs that may possibly prolong QT interval	
The use of the following drugs is permitted (notwithstanding other exclusions and restrictions) provided the patient has been stable on therapy for the periods indicated:
 
Alfuzosin, chloral hydrate, ciprofloxacin, dolasetron, foscarnet, galantamine, gemifloxacin, isradipine, ketoconazole, levofloxacin, mexiletine, nifedipine, octreotide, ofloxacin, ondansetron, quetiapine, ranolazine, telithromycin, tizanidine, vardenafil, venlafaxine, ziprasidone.
 
Amantadine, amitriptyline, amoxapine, clozapine, doxepin, felbamate, flecainide, fluconazole, fosphenytoin, gatifloxacin, granisetron, imipramine, indapamide, lithium, moexipril/HCTZ, moxifloxacin, risperidone, roxithromycin, sertraline, trimethoprim-sulfa, trimipramine, voriconazole.
 
Azithromycin, citalopram, clomipramine, itraconazole, nortriptyline, paroxetine, solifenacin, tacrolimus
 
Fluoxetine, protriptyline, tamoxifen (Appendix J).

AE = Adverse event; BCRP = Breast cancer resistance protein; CYP = Cytochrome P450; ECG = Electrocardiogram.

### 6.5.1 Other Concomitant Treatment

Other medication other than that described above, including denosumab, corticosteroids and/or bisphosphonates for the treatment of bone metastases, which is considered necessary for the patient’s safety and wellbeing, may be given at the discretion of the investigator and recorded in the appropriate sections of the eCRF.

Patients who have received prior treatment with IO therapies should be closely monitored for an appropriate period of time after the last dose of the IO treatment, in accordance with the respective IO label, as immune-mediated adverse reactions with the IO therapy may occur at any time during or after discontinuation of therapy. The stop date of the prior IO drug therapy should be captured in the eCRFs.

### 6.6 Dose Modification

Dose modifications of one or both agents are decided by the investigator (following discussion with AstraZeneca when needed) based on the type of AEs and the known adverse drug reactions for each drug. In case a dose reduction is necessary, the study interventions will be administered as follows:

**Table 7 Dose Reduction for Savolitinib to Manage Adverse Events**

Starting savolitinib dose	CCI
Reduced dose -1	CCI
Reduced dose -2	CCI

Note: Only 2 dose reductions of savolitinib are permitted.

**Table 8 Dose Reduction for Osimertinib to Manage Adverse Events**

Starting osimertinib dose	CCI
Reduced dose -1	CCI

For guidance on dose modifications for management of AEs for savolitinib and osimertinib, see [Appendix I](#).

### 6.7 Intervention after the End of the Study

Patients receiving study intervention at the time of the final DCO will be able to continue to receive study intervention (ie, savolitinib plus osimertinib, savolitinib monotherapy, or osimertinib monotherapy [if savolitinib was stopped earlier]) as long as, in the opinion of the investigator, they are still receiving clinical benefit. Following the final DCO (9 months after the last patient has been randomised), the clinical study database will be closed to new data.

Patients who remain on study intervention after the final analysis will be monitored according to routine clinical practice as defined by the investigator. AstraZeneca will continue to supply study intervention after completion of this study while, in the opinion of the investigator, the patient is benefiting. In the event that product development reaches a point where alternative product supply options become available, then these alternative product supply options will be discussed by AstraZeneca with the investigator. AstraZeneca will work with the investigator to transition the patients to alternative supply, where possible.

Study intervention ongoing at the time of final analysis will be supplied to sites as per ongoing process. Placebo tablets will not be supplied after the final analysis but patients can continue on savolitinib monotherapy as long as, in the opinion of the investigator, they are still receiving clinical benefit and have not reported PD. Drug dispensation and reconciliation will be handled by site on each patient's visit. Paper form process will be used for SAE reporting, all SAEs, overdoses and pregnancies will be reported until 30 days after the last dose. The study will remain open until the last patient is treated. Last patient last visit will be defined as the last patient's treatment discontinuation.

In the event that a roll-over study is available at the time of the final DCO and database closure, patients currently receiving study treatment may be transitioned to such a study, and the current study participation would reach its end. The roll-over study would ensure treatment continuation with visits assessment per its protocol. Any patient that would be proposed to move to such study would be given a new ICF.

## **7 DISCONTINUATION OF STUDY INTERVENTION AND PATIENT DISCONTINUATION/WITHDRAWAL**

### **7.1 Discontinuation of Study Intervention**

It may be necessary for a patient to permanently discontinue (definitive discontinuation) study intervention. If study intervention is permanently discontinued, the patient will remain in the study to be evaluated for survival.

Patients may be discontinued from study intervention in the following situations. Note that discontinuation from study intervention is NOT the same thing as a withdrawal from the study.

- Patient decision. The patient is at any time free to discontinue treatment, without prejudice to further treatment.
- Adverse events.
- Severe non-compliance with the CSP.
- Disease progression as per RECIST 1.1; unless the patient is randomised to savolitinib plus placebo, when cross-over to savolitinib plus osimertinib may be permitted.

- Patients incorrectly initiated on study medication.
- Pregnancy.
- Specific stopping criteria, ie, ILD, acute anaphylaxis or QTcF interval prolongation with signs/symptoms of serious arrhythmia.

See the SoAs ([Table 1](#) and [Table 2](#)) for data to be collected at the time of intervention discontinuation and follow-up and for any further evaluations that need to be completed.

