**Intervention Groups and Duration:**

All patients confirmed as eligible will begin treatment on Day 1 with savolitinib plus osimertinib or savolitinib plus placebo. Treatment will continue **CCl** in 28-day cycles until either objective PD by RECIST 1.1 is assessed, unacceptable toxicity occurs, consent is withdrawn, or another discontinuation criterion is met.

Patients randomised to the savolitinib plus placebo arm may cross-over to open-label savolitinib plus osimertinib following investigator-assessed objective PD to ensure that all patients enrolled may have the opportunity to receive the combination of savolitinib plus osimertinib.

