#### 4.1.1 Randomised Study Design

Prior to CSP V3.0, approximately 56 patients were planned to be randomised in a ratio of 1:1 to receive treatment with CCI savolitinib CCI plus CCI osimertinib CCI or CCI savolitinib CCI plus placebo. At least half of the patients randomised into the study will be second-line patients who were treated with osimertinib as first-line therapy. Randomisation will be stratified according to the number of prior lines of therapy (ie, osimertinib monotherapy as first line or  $\geq$  second line [which includes patients who received osimertinib monotherapy before or after chemotherapy]).

Prospective testing of tumour specimens to determine MET amplification by central FISH using tumour specimens collected after progression on prior treatment with osimertinib should be performed at Pre-screening in advance of Screening for the main study. Patients determined to be MET amplified in Pre-screening will undergo screening during the 28 days prior to randomisation to confirm eligibility ([Sections 5.1](#) and [5.2](#)).

Provision of a FFPE tumour specimen is mandatory (refer to the Laboratory Manual for detailed specimen requirements). This will be used for prospective analysis of MET amplification by FISH.

Patients will continue to receive study medication CCI in 28-day cycles until objective PD by RECIST 1.1 is assessed, unacceptable toxicity occurs, consent is withdrawn or another discontinuation criteria is met ([Section 7](#)). At the time of investigator assessment per RECIST 1.1 of PD, the randomisation blind can be broken and patients who were initially randomised to the savolitinib plus placebo arm will be given the opportunity to cross-over (see [Sections 4.1.2](#) and [6.3](#)). Patients originally randomised to savolitinib plus osimertinib may continue to receive treatment with savolitinib plus osimertinib or osimertinib monotherapy (if savolitinib was stopped earlier) beyond RECIST 1.1 defined PD as long as they continue to receive clinical benefit, in the opinion of the investigator, and do not meet any of the

discontinuation criteria. No other anti-cancer agent is permitted in combination with osimertinib within this study. Patients can continue on savolitinib monotherapy (if randomised to the savolitinib plus placebo arm or if osimertinib was stopped earlier) until objective PD by RECIST 1.1 is assessed. Savolitinib monotherapy post-progression is not permitted.

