### **Continuing on Monotherapy**

If a patient discontinues osimertinib due to toxicity the patient may continue with savolitinib until progression.

If a patient discontinues savolitinib due to toxicity they may continue with osimertinib monotherapy until the Principal Investigator believes there is no further benefit (this may be beyond PD in the absence of clinical symptoms or signs indicating clinically significant PD; no decline in performance status; absence of rapid PD or threat to vital organs or critical anatomical sites [eg, central nervous system metastasis, respiratory failure due to tumour compression, spinal cord compression] requiring urgent alternative medical intervention; or no significant, unacceptable or irreversible toxicities related to study intervention), according to the SoAs ([Table 1](#) and [Table 2](#)).

Following PD, patients may continue on osimertinib monotherapy and continue with all safety assessments as per the SoAs ([Table 1](#) and [Table 2](#)). Savolitinib monotherapy (either if originally randomised to savolitinib plus placebo or after discontinuation of osimertinib if originally randomised to savolitinib plus osimertinib) post progression is not permitted.

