#### **9.4.3 Safety**

Safety and tolerability will be assessed in terms of AEs, SAEs, discontinuation rate due to AEs, deaths, laboratory data, vital signs, ECHO data, ECG data and ECOG performance status. All safety analyses will be performed on the SAS. Data will also be presented separately for patients who crossed over to savolitinib plus osimertinib upon investigator-assessed PD per RECIST 1.1 on savolitinib plus placebo. Safety data will be presented using descriptive statistics unless otherwise specified.

Adverse events will be coded using the most recent version of MedDRA that have been released for execution at AstraZeneca. Adverse events will be graded according to the National Cancer Institute CTCAE (Version 5.0).

The number of patients experiencing each AE will be summarised by the MedDRA system organ class, preferred term and treatment group. The number and percentage of patients with AEs in different categories (eg, causally related, CTCAE Grade  $\geq 3$  etc) will be summarised, and events in each category will be further summarised by MedDRA system organ class, preferred term and treatment group. If there are sufficient SAEs, they will be summarised separately. Further details will be provided in the SAP.

Adverse events occurring prior to the start of study intervention, treatment-emergent AEs and post-treatment emergent AEs will be presented separately. Adverse events occurring in the savolitinib in combination with placebo group will be split into 2 presentations based on whether they occurred before or after the crossover into the savolitinib in combination with osimertinib group.

Any AE occurring before the first dose of study intervention will be included in the data

listings but will not be included in the summary tables of AEs. Adverse event summary tables will include only treatment-emergent AEs. The following events are considered treatment emergent:

- Adverse events with an onset date on or after the first dose of randomised study intervention and within the safety follow-up period (28 days [ $\pm$  7 days] after last dose of all study intervention). Any events in this period that occur after a patient has received further therapy for cancer (following discontinuation of all study intervention) will be flagged in the data listings.
- Worsening of pre-existing events on or after the first dose of study intervention and within the safety follow-up period.

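### Sections 4.1.1 and 4.1.2 let both drugs continue past RECIST progression while Section 7.1 lists progression as a reason to stop in the combination arm; separately, treatment after progression gives the arms unequal adverse event windows

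*Supplement*

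**What the plan says.** **Stopping rule.** The synopsis (1.1, Intervention Groups and Duration) has all patients treated "until either objective PD by RECIST 1.1 is assessed, unacceptable toxicity occurs, consent is withdrawn, or another discontinuation criterion is met". Section 4.1.1 repeats that rule and points to Section 7 for the criteria. It then adds: "Patients originally randomised to savolitinib plus osimertinib may continue to receive treatment with savolitinib plus osimertinib or osimertinib monotherapy" "beyond RECIST 1.1 defined PD as long as they continue to receive clinical benefit, in the opinion of the investigator", on the further condition that no discontinuation criterion is met. Section 4.1.2 gives the same permission, with the same condition, to patients who have crossed over.

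The list in Section 7.1 includes "Disease progression as per RECIST 1.1; unless the patient is randomised to savolitinib plus placebo, when cross-over to savolitinib plus osimertinib may be permitted". Under the sub-heading on continuing with a single drug, 7.1 also says: "Following PD, patients may continue on osimertinib monotherapy and continue with all safety assessments as per the SoAs". The combination is not mentioned there.

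**Adverse event window.** Section 9.4.3 counts as treatment-emergent "Adverse events with an onset date on or after the first dose of randomised study intervention and within the safety follow-up period", and that follow-up period ends 28 (± 7) days after the last dose of all study intervention. Section 9.4.1 cuts savolitinib plus placebo data for patients who cross over at the last assessment before the first combination dose. Section 4.1.2 asks that cross-over after progression take place within 28 days of the progression scan.

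**The concern.** Section 4.1.1 makes continuation depend on a list that contains the very event after which continuation is allowed. The drafters wrote an exception into that list for one arm and none for the other. A site that looks up the rule for a combination patient at progression gets no single answer, and what it decides changes exposure after progression and possibly the time to next therapy, hence overall survival.

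The second issue is related but separate. The combination arm has no cut at progression in the safety analysis, whereas patients who leave savolitinib plus placebo for the combination do have a cut soon after it. Where combination patients are treated after progression, their events keep entering the arm's percentages. Section 9.4.3 plans numbers and percentages of patients, which do not adjust for the length of the window.

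**Working it through.** The plan states no figure on this point, so the check is a comparison of texts followed by a count of days.

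**1. The texts side by side, for patients on both drugs at RECIST progression**

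| Section | What it implies at progression |
|---|---|
| 1.1 | Treatment ends; progression is followed by a reference to another criterion, so it is counted as one |
| 4.1.1 | Same end of treatment, then both drugs (or osimertinib alone) allowed if the patient benefits and meets no discontinuation criterion |
| 4.1.2 | Same allowance and condition after cross-over |
| 7.1, list | Progression is a situation for stopping; only the savolitinib plus placebo arm is excepted |
| 7.1, monotherapy text | Osimertinib alone may continue; silent on the combination |
| 6.7 (after the final data cut-off) | Study treatment may continue with clinical benefit; absence of progression is added as a condition for savolitinib monotherapy only |

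**2. One patient taken through the rules.** Take a patient randomised to the combination, on both drugs at first progression, whom the investigator judges to benefit. Section 4.1.1 allows both drugs if no criterion is met. Section 7.1 lists progression without excepting this arm, but its lead-in only says that patients may be discontinued. One site could stop both drugs, another could continue both, and a third could keep osimertinib alone. Each could cite the protocol.

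**3. Length of the adverse event window after progression.** Let k be the number of further 28-day cycles in the combination arm, and g the days from progression scan to first combination dose in a savolitinib plus placebo patient who crosses over at progression.

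- Combination arm: 28 × k + 28 (± 7) days.
- Savolitinib plus placebo, crossing over at progression: g days, with g at most 28 if 4.1.2 is followed.

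| k (illustrative) | Combination arm, days | Crossed over at progression, days |
|---|---|---|
| 0 | 28 (21 to 35) | up to 28 |
| 1 | 28 + 28 = 56 (49 to 63) | up to 28 |
| 3 | 84 + 28 = 112 (105 to 119) | up to 28 |

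If treatment stops at progression, the two windows are of similar length. The inequality appears with treatment after progression and grows by 28 days per cycle. Because the window runs from the last dose of all study intervention, osimertinib alone after progression extends it too.

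**4. Why this is not turned into percentage points.** That would need the event rate after progression, the distribution of k, the share of the arm that progresses and stays on treatment before the data cut-off, and the share that already had an event. The documents give none of these. At the planned 28 per arm, one patient is 1/28 = 3.6 percentage points, and enrolment will fall short of plan, so each patient will weigh more.

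**5. Efficacy endpoints.** ORR uses data up to progression (9.4.2.1), and PFS and DoR end at the progression event or at death (9.4.2.2). Their definitions do not depend on treatment after progression.

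**The case against.** The list in 7.1 is not a set of mandatory stops. It also contains adverse events without qualification, yet Table I1 continues both drugs at Grade 2 or lower. The same section accepts osimertinib beyond progression. The text naming osimertinib alone stands under a monotherapy heading, so its silence on the combination is a matter of scope and not a prohibition. Sections 4.1.2 and 6.7 both point towards allowing continuation.

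All of this stands, and it rules out some stronger readings that a reader might infer:

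- That the condition in 4.1.1 can never be met. This holds only if every item in 7.1 is a bar to treatment, which the lead-in does not say.
- That every progressing combination patient meets the conflict. It concerns those still on both drugs and judged to benefit; patients who stopped savolitinib for toxicity are covered explicitly.
- That savolitinib plus placebo patients who cross over add no events after progression. Their data are cut before the first combination dose, not at progression, so events in the gap of up to 28 days count.

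A further objection is that the unequal windows do not come from the wording conflict. That is correct: they come from 9.4.1 and 9.4.3, and would remain if 4.1.1 were confirmed as written. Safety is descriptive, 9.4.3 splits savolitinib plus placebo events at cross-over, adds tables for the first 6 weeks, summarises exposure, and leaves detail to an SAP that is not shown. These help the reader, but none aligns the arms at progression. The missing detail is not itself a fault; the request is for one addition while the SAP can still take it.

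**Conclusion.** Two separate points hold, and both should be dealt with.

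First, Sections 1.1, 4.1.1, 4.1.2 and 7.1 do not give one rule for patients on both drugs at RECIST progression. The permissive lead-in to 7.1 and the lean of 6.7 soften the conflict but do not remove it: 4.1.1 turns on whether a criterion is met, and 7.1 excepts only the other arm. Which rule should apply is for the sponsor to decide.

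Second, whenever combination patients are treated after progression, plain adverse event percentages compare unequal windows: 28 days more per further cycle in that arm, against at most 28 days from the progression scan in patients who cross over at progression as planned.

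The effect on the percentages cannot be fixed from the documents, and any figure in percentage points would rest on invented inputs. An effect on overall survival through time to next therapy is possible but equally unsized. The ORR, PFS and DoR definitions are untouched.

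**What to change.** 1. **Protocol wording.** Reconcile 1.1, 4.1.1, 4.1.2 and 7.1 into one statement of what may continue after RECIST progression in patients on both drugs, with no condition that refers back to progression. The cost is amendment wording.

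2. **Safety tables.** Before unblinding, when the SAP is due to be finalised (9.4), add to 9.4.3 or the SAP a supplementary adverse event overview and a Grade 3 or higher table. Cut both arms at first RECIST progression, or at last dose plus the safety follow-up if that is earlier, and show events after progression separately. Patients who cross over without progression after the study is unblinded stay cut before their first combination dose under 9.4.1; state how many there are. The cost is one repeat set of tables, since progression and event onset dates are already collected.

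The cut aligns the rule, not the time at risk: time to progression may itself differ between arms, so read these tables beside the exposure summary that is already planned.
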